8.5.1 Pharmacokinetics

Refer to relevant module for information on PK.

8.5.2 Pharmacodynamics

Refer to relevant module for information on pharmacodynamics.

8.5.3 Immunogenicity Assessments

Refer to relevant module for information on immunogenicity assessments.

8.6

CCI

Refer to relevant module for information on CCI

.

8.7 Optional Genomics Initiative Sample

Collection of optional samples for genomics initiative research is also part of this study as specified in the SoA and is subject to agreement in the ICF addendum. A CCI sample for DNA isolation will be collected from participants who have consented to participate in the genetic analysis component of the study. Participation is optional. Participants who do not wish to participate in the genetic research may still participate in the study. This CCI sample will be taken from consenting participants prior to AZD4573 dosing.

See [Appendix D](#) for information regarding the Genomics Initiative genetic sample. Details on processes for collection and shipment and destruction of these samples can be found either in the appendices or in the Laboratory Manual.

For storage and destruction of genetic samples see [Appendix D](#).

8.8 Health Economics

Not applicable for study.

9 STATISTICAL CONSIDERATIONS

The statistical analyses will be performed by AstraZeneca or CRO under the direction of the Early Biometrics Oncology, AstraZeneca. A comprehensive SAP will be prepared.

9.1 Statistical Hypotheses

Not applicable.

9.2 Sample Size Determination

Refer to relevant module for information on sample size determination.

9.3 Populations for Analyses

Refer to relevant module for information on populations for analyses.

9.4 Statistical Analyses

The SAP will be finalised prior to database lock and will include a more technical and detailed description of the statistical analyses described in this section. This section is a summary of the planned statistical analyses of the most important endpoints including primary and key secondary endpoints. Any deviations from this plan will be reported in the CSR.

9.4.1 General Considerations

Unless stated otherwise, each module and cohort will be analysed separately. Data will be presented by cohort. Descriptive statistics will be used for all variables. Continuous variables will be summarised by the number of observations, mean, standard deviation, median, minimum, and maximum. Geometric mean and coefficient of variation may be presented as applicable. Categorical variables will be summarised by frequency counts and percentages for each category. Unless otherwise stated, percentages will be calculated from the population total, by cohort and by timepoint as appropriate. Time to event variables will be presented using the KM methodology where appropriate, including median time calculated from the KM curves. SAS® version 9.4 (as a minimum) will be used for analyses presented in the CSR.

Depending on the extent of any impact, summaries of data relating to participants diagnosed with COVID-19, and impact of COVID-19 on study conduct (in particular missed visits, delayed or discontinued study treatment, and other protocol deviations) may be generated. More details will be provided in the SAP.

Refer to the relevant Module for details on analyses and cut-off triggers.

9.4.2 Efficacy Analyses

Analysis of Primary Endpoint (Efficacy)

The primary objective of this study is to assess the efficacy of the module-defined study treatment in participants with r/r PTCL or r/r cHL. Endpoints for this objective are specific to each module.

For information on efficacy analyses and endpoints, refer to the relevant module.

9.4.3 Safety Analyses

Safety and tolerability will be assessed in terms of AEs, laboratory data, vital signs, and ECG changes. These variables will be collected for all participants. All safety data listings and summaries will be created using the safety analysis set.

Adverse events will be listed individually by cohort and participant. The number of participants experiencing each AE will be summarised by the MedDRA system organ class, MedDRA preferred term, and CTCAE grade (in line with NCI CTCAE Version 5.0). TLS will be graded by CTCAE grade and Howard's modification of Cairo-Bishop grading ([Appendix G; Howard et al 2011](#)). The number and percentage of participants experiencing each AE, and the number and percentage of participants with AEs in different categories (eg, causally related and CTCAE Grade ≥ 3) will be summarised by cohort, and events in each category will be further summarised by MedDRA system organ class and preferred term. SAEs will be summarised separately if a sufficient number occur.

Adverse event summary tables will include only treatment-emergent AEs. Adverse events will be defined as treatment-emergent if they have an onset or worsen (by investigator report of a change in intensity/severity), during the study treatment until the follow-up period (as defined in the individual study Modules), but prior to subsequent cancer therapy. AEs occurring outside of this period will be listed but not summarised.

During the evaluation of the AE data, an AstraZeneca medically qualified expert will review the list of AEs that were not reported as SAEs and AEs leading to discontinuation of study treatment. Based on the expert's judgement, AEs of particular clinical importance may, after consultation with the Global Safety Physician, be considered OAEs and reported as such in the CSR. A similar review of laboratory values, vital signs, ECGs, and other safety assessments will be performed for identification of OAEs.

Examples of these could be marked haematological and other laboratory abnormalities, and certain events that lead to intervention (other than those already classified as serious), dose reduction, or significant additional treatment. Duration of exposure will be summarised.

Haematology, serum chemistry, vital signs, ECG data, and other laboratory values will be listed individually by cohort and participant, and suitably summarised. For all laboratory variables, which are included in the current version of CTCAE, the CTCAE grade will be calculated.

Details of any deaths will be listed for all participants.

Graphical presentations of safety data will be presented as is deemed appropriate. This may include, but is not restricted to, presentation of parameters against time, concentration or shift plots. Appropriate scatter plots will also be considered to investigate trends in parameters compared to baseline level.

9.4.4 Pharmacokinetic Analyses

Assessment of the plasma PK of AZD4573 as monotherapy and in combination with other module-defined anti-cancer agents when given in combination is a secondary objective for the study.

The endpoints for these analyses are plasma concentrations and derived PK parameters for AZD4573 summarised by cohort for the PK analysis set. Plasma/serum concentrations and derived PK parameters for other anti-cancer agents may be summarised by cohort for the PK analysis set, as applicable.

For details on PK analyses, please refer to the separate Bioanalytical Report.

9.4.5 Pharmacodynamics [CC1] Analyses

Assessment of pharmacodynamics [CC1] analyses are exploratory objectives for this study.

For details on pharmacodynamic analyses [CC1] analyses refer the relevant module.

9.5 Interim Analyses

See relevant module for information on planned interim analyses.

9.6 Data Monitoring Committee

There will be no formal data monitoring committee for this study. See relevant module for information regarding the use of a SRC for this study.

[figure not shown]
10 MODULE 1

10.1 Summary – Module 1

10.1.1 Schema

Figure 5 Module 1 Schema: AZD4573 Monotherapy in Participants with r/r PTCL and r/r HL

AZD4573 Monotherapy Treatment

^a Dosing regimen based on AZD4573 monotherapy RP2D in lymphoma = 12 mg weekly.

^b Dose confirmation in first 6 participants/cohorts (safety/PK/PD) → SRC. Additional dose levels may be explored depending on the emerging clinical data in PTCL/cHL.

^c Twenty-one participants per cohort, and **CCI**

CCI

^d Twenty-one participants per cohort, and **CCI**

CCI

^e Primary analysis at N = 21 for each cohort, with the primary analysis after approximately 6 months or when 75% of participants have progressed or died (Section 10.6). Additional data cuts may also be performed if required.

Abbreviations: AE, adverse event; ALCL, anaplastic large cell lymphoma; BV, brentuximab vedotin; cHL, classical Hodgkin Lymphoma; CR, complete response, CTCAE, Common Terminology Criteria for Adverse Events; CTCL, cutaneous T-cell lymphoma; DCO, data cut-off; ECG, electrocardiogram; ECOG, Eastern Cooperative Oncology Group; N, number; NK PTCL, natural killer/peripheral T-cell lymphoma; ORR, overall response rate; PD, pharmacodynamic; PR, partial response; PTCL, peripheral T-cell lymphoma; r/r, relapsed/refractory; RP2D, recommended phase II dose.

10.1.2 Schedule of Activities

Table 9 Schedule of Activities: Module 1 (AZD4573 Monotherapy)

Procedure	Screening ^a	Cycle 1, Weeks 1-5 (includes intra- participant Dose ramp-up)	Cycle 2 to 12 (Cycle = 21 Days)			Cycles 13+ (Cycle = 21 days)	Disease Assessment	30-Day FU ^e	LTFU	Details in Section					
			Days												
			1	8	15										
		(± 2 Days)	(± 2 Days)			(± 7 Days)	(± 7 Days)	(± 7 Days)							
Informed consent ^b	X									Appendix A					
Inclusion/exclusion	X									5 and 10.4.3					
Medical history and demographics	X									5 and 10.4.3					
Physical examination	X	X	X	X	X	X		X		10.8.2.1					
ECOG performance status	X	X	X	X	X	X		X		10.8.2.1					
B symptoms	X	X	X	X	X	X		X		10.8.2.2					
Vital signs and weight	X	X	X	X	X	X		X		10.8.2.3					
12-lead ECG	X	Refer to Section 10.8.2.4 for schedule						X		10.8.2.4					
ECHO/MUGA	X	As clinically indicated						X		10.8.2.4					
Cardiac troponin	X	X	X			X		X		10.8.2.5					
T4, Cortisol, ACTH and TSH	X							X		10.8.2.5					
EBV	Prior to receiving study treatment									10.8.9.2					

Table 9 Schedule of Activities: Module 1 (AZD4573 Monotherapy)

Procedure	Screening ^a	Cycle 1, Weeks 1-5 (includes intra- participant Dose ramp-up)	Cycle 2 to 12 (Cycle = 21 Days)			Cycles 13+ (Cycle = 21 days)	Disease Assessment	30-Day FU ^e	LTFU	Details in Section					
			Days												
			1	8	15										
			(± 2 Days)	(± 2 Days)		(± 7 Days)	(± 7 Days)	(± 7 Days)							
Haematology ^c	X	X	X	X	X	X		X		10.8.2.5					
Coagulation	X	X	X	X	X	X		X		10.8.2.5					
Clinical chemistry ^c	X	X	X	X	X	X		X		10.8.2.5					
Urinalysis	X	X	X			X		X		10.8.2.5					
TLS monitoring (for at least 24 hours post SOI)	X	X								10.6.2.1.2					
Pregnancy testing (WOCBP)	X	Pre-dose Week 1, Day 1	Prior to initiating a new cycle (once every 21 days)					X		10.8.2.5					
Lipase/amylase	X	X	X	X	X	X		X		10.8.2.5					
Hepatitis serology	X									10.8.2.5					
Liver chemistry tests	X									10.8.2.5					
Whole blood samples for CCI	X	Per Section 10.8.8.4					X	X		10.8.8.4					
CCI sample for CCI		Prior to receiving study treatment								10.8.9.4					

Table 9 Schedule of Activities: Module 1 (AZD4573 Monotherapy)

Procedure	Screening ^a	Cycle 1, Weeks 1-5 (includes intra- participant Dose ramp-up)	Cycle 2 to 12 (Cycle = 21 Days)			Cycles 13+ (Cycle = 21 days)	Disease Assessment	30-Day FU ^e	LTFU	Details in Section
		Cycle 1 Weeks 1-5, Day 1 Visits	Days			Day				
			1	8	15	1				
			(± 2 Days)	(± 2 Days)		(± 7 Days)	(± 7 Days)	(± 7 Days)		
Serum immunoglobulins (IgA, IgM, IgG)	X		Day 1 of Cycles 3, 6 and 9 (pre-dose)			Cycle 13 (± 7 days) and every 6 months thereafter		X		10.8.2.6
Concomitant medication	X	X	X	X	X	X		X	X	5.2, 6.5
Adverse event evaluation		X	X	X	X	X		X	X	8.3
AZD4573 plasma PK		Refer to Section 10.8.6 for schedule								10.8.6
CCI [REDACTED]		X								10.8.6
Pharmacodynamic samples (blood) for AZD4573		Weeks 1 to 3								10.8.7
CCI [REDACTED]	X	Weeks 1 to 3	If elevated liver chemistry tests/bilirubin							10.8.9.3
Exploratory analyses samples	X	Refer to Section 10.8.8 for schedule								10.8.8

Table 9 Schedule of Activities: Module 1 (AZD4573 Monotherapy)

Procedure	Screening ^a	Cycle 1, Weeks 1-5 (includes intra- participant Dose ramp-up)	Cycle 2 to 12 (Cycle = 21 Days)			Cycles 13+ (Cycle = 21 days)	Disease Assessment	30-Day FU ^e	LTFU	Details in Section
		Cycle 1 Weeks 1-5, Day 1 Visits	Days			Day				
			1	8	15	1				
			(± 2 Days)	(± 2 Days)		(± 7 Days)	(± 7 Days)	(± 7 Days)		
Genomics Initiative sample (optional)		X								8.7
Bone marrow biopsy & aspirate (PTCL only) ^d	X						As clinically indicated and to confirm CR			10.8.9.1.1
Fresh or archival tumour tissue sample	X									10.8.9.1.2
Additional tumour biopsy sample (optional)							At disease progression	(X)		10.8.9.1.2
Disease assessments/radiologic scans	X		After Cycle 2 (+/- 1 week), then Q9W until W26 (Cycle 8, Week 3), then Q12W (+/- 1 week)					X		10.8.1
AZD4573 (IV; once weekly) ^c		X	X	X	X	X				10.6
Disease progression follow-up (SoC)									X	8.2.2

Table 9 Schedule of Activities: Module 1 (AZD4573 Monotherapy)

Procedure	Screening ^a	Cycle 1, Weeks 1-5 (includes intra- participant Dose ramp-up)	Cycle 2 to 12 (Cycle = 21 Days)			Cycles 13+ (Cycle = 21 days)	Disease Assessment	30-Day FU ^e	LTFU	Details in Section
		Cycle 1 Weeks 1-5, Day 1 Visits	Days		Day					
			1	8	15	1				
		(± 2 Days)	(± 2 Days)		(± 7 Days)	(± 7 Days)	(± 7 Days)	(± 7 Days)		
Survival FU ^e									X	8.2.3

^a Screening tests should be performed within 30 days before the first administration of study drug, unless otherwise indicated.

^b Informed consent must be obtained ≤ 30 days before first dose of study drug and must be obtained before any protocol-defined screening tests are done.

^c Results of safety laboratory testing (haematology and clinical chemistry at a minimum) must be available within 72 hours prior to dosing and must be reviewed by the investigator prior to each administration of AZD4573. To initiate Cycle 1 and subsequent cycles, haematology and chemistry criteria in inclusion criteria 10, 13, and 14 shall be met. In addition, during AZD4573 treatment, dose modification and discontinuation guidelines are provided in Section 10.6.1.

^d Mandatory exploratory CCI analysis will be performed any time a bone marrow analysis is performed.

^e The follow-up visit will be performed 30 days (± 7 days) after the last dose of all study drug. Disease assessments will be repeated at this visit if they have not been performed within 9 weeks if the participant discontinued before Week 26, or 12 weeks if the participant discontinued after Week 26.

Abbreviations: ACTH, adrenocorticotrophic hormone; ECG, electrocardiogram; ECHO, echocardiogram; ECOG, Eastern Cooperative Oncology Group; FU, follow-up; IgA, immunoglobulin A; IgG, immunoglobulin G; IgM, immunoglobulin M; IV, intravenous; LTFU, long-term follow-up; MUGA, multigated acquisition; PK, pharmacokinetic; PTCL, peripheral T-cell lymphoma; SoC, standard of care; SOI, start of infusion; TLS, tumour lysis syndrome; TSH, thyroid stimulating hormone; WOCBP, women of childbearing potential.

10.2 Introduction – Module 1

Module 1 of this study will evaluate the efficacy, safety, and tolerability of AZD4573 monotherapy in participants with r/r PTCL or r/r cHL. For an overview of the study design see [Figure 5](#).

10.3 Objectives and Endpoints – Module 1

Type	Objectives	Endpoints
Primary		
Efficacy	To assess the efficacy of AZD4573 by evaluation of objective response rate.	
Endpoint based on Lugano response criteria for malignant lymphoma (Cheson et al 2014):
– ORR, defined as the proportion of participants who have a tumour response (CR and PR)^a
Secondary		
Efficacy	To assess efficacy of AZD4573 by evaluation of tumour response and OS.	
Endpoints based on Lugano response criteria for malignant lymphoma (Cheson et al 2014):
– CR rate– DoR– PFSOS
Safety	To assess the safety and tolerability of AZD4573.	
Adverse events, laboratory data, vital signs, and ECG changes.
 
Assessments related to AEs cover:
 
• Occurrence/frequency• Relationship to IP as assessed by investigator• CTCAE grade• SAEs• Death• AEs leading to discontinuation of IP• AEs leading to dose modifications• AESIs

PK	To assess the plasma PK of AZD4573.	
 • Plasma concentrations and derived PK parameters for AZD4573
Exploratory		
PD	To assess the pharmacodynamics of AZD4573.	
 • CCI [REDACTED] • CCI [REDACTED] • CCI [REDACTED]
CCl	CCl [REDACTED]	
 • CCI [REDACTED]
CCl	CCl [REDACTED]	
 • CCI [REDACTED]
Genetics	To collect and store CCI [REDACTED] a CCI [REDACTED] sample, for future exploratory research CCI [REDACTED]	
 • CCI [REDACTED]

^a By investigator assessment; however, if preliminary results suggest a major advance over available therapy, AstraZeneca will consult with relevant Health Authorities to agree on modifications to the protocol and will conduct blinded independent central review of ORR.

Abbreviations: AE, adverse event; CCI [REDACTED]; CR, complete response; CTCAE, Common Terminology Criteria for Adverse Events; DoR, duration of response; ECG, electrocardiogram; IP, investigational product; CCI [REDACTED] 1; MTD, maximum tolerated dose; ORR, overall response rate; OS, overall survival; CCI [REDACTED]; PD, pharmacodynamics; PFS, progression-free survival; PK, pharmacokinetics; PR, partial response; CCI [REDACTED]; SAE, serious adverse event; TTR, time to response.

10.4 Study Design – Module 1

This is a modular, Phase II, multicentre, open-label dose confirmation and expansion study. Module 1 will assess the efficacy of AZD4573 as a monotherapy in r/r PTCL and r/r cHL populations. For an overview of the study design see [Figure 5](#).

- AZD4573 will be administered intravenously as a monotherapy to participants with r/r PTCL or r/r cHL, including an intra-participant dose ramp-up. For dose regimen, see Section 10.4.1 below.
- For details on study design applying to all modules, including information on the SRC and the definitions for end of study, refer to the core protocol study design (Section 4.4).

[figure not shown]
10.4.1 Module 1 Design: AZD4573 monotherapy

Module 1 is non-randomised and will consist of 2 r/r PTCL cohorts and 1 r/r cHL cohort; see Figure 5 and Table 10 below for planned participant numbers.

Each cohort will include an intra-participant dose ramp-up, starting at 6 mg AZD4573 (Figure 6). The target dose following the ramp-up is 12 mg attained on Week 3 of Cycle 1. During the first cycle, participants will receive a single dose of AZD4573 once weekly beginning with 6 mg Week 1, 9 mg Week 2, and 12 mg for each of Weeks 3 to 5.

Every cycle beyond Cycle 1 will be 3 weeks in length and participants will receive 12 mg infusions of AZD4573 once weekly until progression.

Figure 6 **Module 1 AZD4573 Monotherapy Dosing Regimen in PTCL and cHL including Intra-Participant Dose Ramp-Up**

Abbreviations: cHL, classical Hodgkin Lymphoma; D, day; PTCL, peripheral T-cell lymphoma; Q1W, once weekly.

A comprehensive initial review of all safety and PK/PD data will be conducted in approximately the first 6 participants of each cohort (safety run-in), with separate SRCs for each cohort executed independently. The safety assessment will be undertaken by the SRC and is detailed in Section 10.4.4. The study procedures and safety assessments undertaken for the first cycle will be as per the SoA (Table 9). Each cohort will have a separate dose confirmation, assessed independently by the SRC, to assess safety and PK/PD data compared to the known profiles in the first time in human study (Study D8230C00001) lymphoma population.

These SRC reviews will confirm whether the RP2D for lymphoma (IV infusion 12 mg once weekly, including intra-participant ramp-up) is safe and tolerable or if additional dose optimisation is indicated at a revised dose and/or schedule. All cohorts can be opened and delivered independently of each other.

The role and responsibilities of SRC members, as well as the purpose and timing of the SRC meetings are described in the SRC Charter.

In addition to the initial safety run-in evaluation conducted separately within each cohort, pooled safety monitoring will be conducted every three months after the initial 15 dosed patients, pooled across the three cohorts, have had an opportunity to be treated for at least 8 weeks. If > 25% of participants experience any AEs related to study intervention that result in discontinuation of study treatment, the study data will be evaluated by the SRC. Enrolment may be paused until the safety data review by the SRC has been completed.

Other criteria for stopping or pausing the recruitment are described in Section 7.1.1.

CCI

If 1 or more cohorts show a favourable safety and efficacy profile by the primary analysis then further expansion cohorts may be added via a protocol amendment. The DCO for the primary analysis for each cohort will occur after all response-evaluable participants in the cohort have had the opportunity to be followed for at least 6 months since their first dose or have progressed or have initiated other anticancer therapy, or when 75% of participants have progressed or died, whichever occurs first. Additional data cuts may also be performed if required.

Table 10 Module 1: Planned Response-Evaluable Participant Population

Cohort	Population	Number of participants ^a	Line of therapy
Cohort 1	PTCL, all comers (excluding NKTCL)	21	2+
Cohort 2	PTCL (NKTCL only)	21	2+
Cohort 3	cHL	21	3+

^a CCI

Abbreviations: cHL, classical Hodgkin Lymphoma; NKTCL, natural killer/T-cell lymphoma; CCI [REDACTED]; PTCL, peripheral T-cell lymphoma.

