5.2 Exclusion Criteria

The below are the core exclusion criteria for all modules of the study; all participants must meet the criteria described in the relevant module in addition to those described below. Where module-specific criteria are more stringent than core study criteria, the module-specific criteria take precedent.

Participants are excluded from the study if any of the following criteria apply:

Type of Participant and Disease Characteristics

- 1 **PTCL only:** Presence of bulky disease (defined as largest lymphoma lesion ≥ 10 cm) or a LDH value $> 3 \times$ ULN.
- 2 **PTCL only:** Diagnosis of any of the following:
 - (a) Lymphoblastic/precursor T-cell lymphoma or leukaemia
 - (b) T-cell prolymphocytic leukaemia
 - (c) T-cell large granular lymphocytic leukaemia
 - (d) Cutaneous T-cell lymphoma (eg, primary cutaneous type ALCL, mycosis fungoide/Sezary syndrome).

Medical Conditions

- 3 With the exception of alopecia and neuropathy, presence of any unresolved non-haematological toxicities from prior therapy greater than CTCAE Grade 1 at the time of starting study treatment.
- 4 Presence of, or history of, CNS lymphoma, leptomeningeal disease, or spinal cord compression.
- 5 History of prior non-haematological malignancy except for the following:

- (a) Malignancy treated with curative intent and with no evidence of active disease present for more than 1 year prior to screening and felt to be at low risk for recurrence by treating physician.
- (b) Adequately treated lentigo maligna melanoma without current evidence of disease or adequately controlled non-melanomatous skin cancer.
- (c) Adequately treated carcinoma in situ without current evidence of disease.

6 As judged by the investigator, any evidence of:

- (a) Severe or uncontrolled systemic disease (eg, severe hepatic impairment, interstitial lung disease [bilateral, diffuse, parenchymal lung disease]).
- (b) Current unstable or uncompensated respiratory or cardiac conditions.
- (c) Uncontrolled hypertension.
- (d) Uncontrolled active systemic fungal, bacterial, viral, or other infection (defined as exhibiting ongoing signs/symptoms related to the infection and without improvement, despite appropriate antibiotics or other treatment).
- (e) IV anti-infective treatment within 1 week before first dose of study drug.

7 Known history of infection with HIV.

8 Serologic status reflecting active hepatitis B or C infection:

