10.4.4 Safety Review Committee

A study-specific SRC will provide ongoing safety surveillance of the study, with regularly scheduled reviews of safety, PK, and other relevant data.

The SRC will be responsible for making recommendations for dose confirmation or modification. All participants will be followed for safety through the entire duration of treatment.

A comprehensive initial review of all safety data will be conducted in approximately the first 6 participants of each cohort (safety run-in), with separate SRCs for each cohort executed independently. Recruitment will not be paused during this review. These participants will be

followed until all have completed Cycle 1, to ensure the treatment schedule is safe and tolerable. The SRC will review the totality of all relevant data (eg clinical, laboratory, safety) prior to providing decisions on study conduct. All decisions by this committee will be documented and shared in writing with all participating sites.

If, on an ongoing basis, > 25% of participants experience any AEs related to study intervention that result in discontinuation of study treatment, study data will be evaluated by the SRC. Enrolment may be paused until the safety data review by the SRC has been completed. Following this SRC review, additional monitoring may be implemented and/or enrolment and dosing may resume at a lower dose level or on a modified schedule. The SRC will meet at least every 6 months to review the overall safety and clinical data from the study.

At any time point during the study, the occurrence of a fatal AE deemed related to study therapy (after full etiological work-up and in discussion with the SRC) will result in study drug interruption and a comprehensive review of safety.

10.5 Study Population – Module 1

Refer to Section 5.1 and Section 5.2 in core protocol for inclusion and exclusion criteria, respectively.

10.6 Study Intervention – Module 1

AZD4573 is administered as an absolute (flat) dose, 2-hour (\pm 15 minutes) intravenous infusion on a once weekly schedule. CCI

Arm name	N/A
Intervention name	AZD4573
Type	Drug
Dose formulation	Concentrate for solution for infusion
Unit dose strength(s)	1.5 mg/ml
Dosage level(s)	6 mg AZD4573 (starting dose) 9 mg AZD4573 12 mg AZD4573 (target dose)
Route of administration	IV infusion
Use	Experimental
IP or NIP	IP
Sourcing	Provided centrally by the sponsor

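### After the Cycle 1 run-in, the only scheduled numerical safety trigger in the visible text is pooled over three diseases, so it can stay silent when one cohort has a high rate of related discontinuation

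*Protocol*

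**What the plan says.** Protocol 10.4.1 treats the three diseases as separate dose questions: "Each cohort will have a separate dose confirmation, assessed independently by the SRC", and "All cohorts can be opened and delivered independently of each other". The run-in behind that confirmation is described in 10.4.4. It covers about the first 6 participants of each cohort, who are "followed until all have completed Cycle 1, to ensure the treatment schedule is safe and tolerable". It states no numerical limit, and "Recruitment will not be paused during this review".

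After the run-in, 10.4.1 adds that "pooled safety monitoring will be conducted every three months after the initial 15 dosed patients, pooled across the three cohorts". The clock for this starts once those 15 have each had the chance of 8 weeks on treatment. The next sentence gives the trigger: if more than 25% of participants have related adverse events (AEs) that lead to discontinuation, the SRC evaluates the data and enrolment may be paused.

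Sections 7.1.1 and 10.4.4 repeat the 25% rule on an ongoing basis. Neither says whether it is pooled or per cohort, and neither gives a minimum number or a denominator. Under 10.4.4, after such a review "enrolment and dosing may resume at a lower dose level or on a modified schedule".

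Other safeguards are stated: single-event pause criteria and a sponsor decision on undue risk (7.1.1), SRC meetings at least every 6 months (10.4.4), expedited reporting of AEs of special interest (8.3.6) and individual dose-modification rules (10.6.1).

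**The concern.** The dose is confirmed by cohort, but the scheduled numerical check that follows is not. The cohorts may differ in tolerability: section 5.2 excludes bulky disease and high LDH for PTCL only, and line of therapy is 2+ for PTCL and 3+ for cHL. If one disease tolerates the dose badly, two better-tolerating cohorts dilute its discontinuations in the pooled percentage.

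What would be lost is the automatic SRC evaluation, the step that can lead to a lower dose or a modified schedule. The likely consequence is a later dose review in one disease. The ORR analysis by cohort is not affected.

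A second, smaller problem needs no assumption about toxicity. One trigger is worded in two ways in three sections, and none of them fixes the denominator, so two people could apply it to the same data and disagree.

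**Working it through.** The plan states no operating characteristics for the 25% rule, so there is no figure of its own to reproduce.

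**Inputs from the protocol.** Threshold above 25%, pooled, first look at 15 dosed (10.4.1); 21 response-evaluable per cohort, 63 in all (10.9.2); run-in of about 6 per cohort (10.4.4).

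**Assumed, because the documents give nothing.** One cohort has a true related-discontinuation rate of 40% and the other two have rate q = 5, 10, 15 or 20%. Looks fall at 15/30/45/63 dosed with equal accrual. Every participant's status is known at each look.

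**Step 1, expected pooled rate.** With equal cohorts it is (40 + 2q)/3 = 16.7, 20.0, 23.3 and 26.7%. For the expected rate to pass 25%, the third cohort must exceed 75 − 2q = 65, 55, 45 or 35%.

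**Step 2, first look.** The rule needs at least 4 events in 15. For q = 10%, the chance of 3 or fewer from Bin(5, 0.4) + Bin(10, 0.1) is 0.0778×0.9872 + 0.2592×0.9298 + 0.3456×0.7361 + 0.2304×0.3487 = 0.653.

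**Step 3, all looks.** Carrying the surviving distribution forward to 8 of 30, 12 of 45 and 16 of 63 gives the chance that the rule never fires. Exact convolution and simulation agree.

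| Reading of the rule | q = 5% | 10% | 15% | 20% |
|---|---|---|---|---|
| Scheduled pooled check, balanced accrual | 75% | 56% | 35% | 19% |
| Same, affected cohort at half speed, continuing to 21 | 90% | 70% | 45% | 24% |
| Ongoing rule, pooled after every participant, from the 6th dosed | 54% | 36% | 21% | 10% |
| Same, from the 15th dosed | 70% | 48% | 28% | 14% |
| Balanced, adding any cohort above one third from 12 dosed | 27% | 24% | 18% | 12% |
| Balanced, adding any cohort above 25% from 12 dosed | 6% | 5% | 3% | 2% |

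**Step 4, cost.** The chance of at least one review when all three cohorts share a true rate of 5/10/15/20%:

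- Pooled check alone: 0.6/6/21/46%.
- With the one-third cohort limit: 0.6/6/23/49%, at most about 4 points more (about 5 with a slow cohort).
- With a 25% cohort limit: 2/19/51/79%.

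**Step 5, credit for the run-in.** Suppose the SRC acted on 2 related discontinuations in 6 (assumed; the protocol sets no number). At 40%, P(X ≥ 2) = 1 − 0.6⁶ − 6×0.4×0.6⁵ = 77% if every event falls in Cycle 1. If half do, the rate is 20% and the probability is 34%. The run-in and the balanced pooled check then both miss in 23/21/16/10% or 55/43/29/16% of trials.

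**Step 6, denominator.** At an assumed 3 participants a month, about 20 have been dosed when the 15th reaches 8 weeks. Four events among the first 15 are 4/15 = 26.7% (met). Over all dosed they are 4/20 = 20.0% (not met). At 2 to 6 a month the all-dosed figure runs from 4/18 = 22.2% to 4/26 = 15.4%.

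**The case against.** The strongest reply is that a silent trigger is not a missed signal. A reader might infer from 75% that a toxic cohort would go unseen, and the documents do not support that. The three-monthly monitoring takes place whether or not 25% is crossed. The SRC meets at least every 6 months, and the trial is open-label. Related deaths, confirmed Hy's law cases, TLS of grade 4 or higher not reversed within 48 hours and unexpected life-threatening events can each pause recruitment. The trigger itself requires only an evaluation. All of this stands, and it limits the harm to a possible delay, which these figures do not measure in months or participants.

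The rates are assumed. The 75% end needs an eight-fold difference between cohorts on the same drug and dose, and the eligibility differences do not establish one that large. That also stands, so the range should be read as a whole.

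The ongoing rule may already be meant per cohort, which would largely close the gap. Text after the rule in 10.4.1 is redacted and the SRC Charter was not supplied. The point is therefore limited to visible text.

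A reader might also infer that a slowly enrolling cohort would stay too small for any cohort limit to operate. The documents plan 21 response-evaluable participants in every cohort, each with its own primary analysis. Continued to 21, a half-speed cohort is caught about as well by a 25% cohort limit starting at 15 as by one starting at 12 (miss about 5/5/3/2% for either).

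Pooling has merit for a drug effect common to all three diseases, so the pooled check should stay.

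**Conclusion.** The gap is real in the visible text. After a small run-in with no stated limit, the only scheduled numerical trigger averages over three diseases whose doses the protocol confirms separately. With one cohort at 40% and the others at 5% to 20%, it never fires in 75% down to 19% of trials under balanced accrual. The most favourable pooled reading calculated (the ongoing rule after every participant from the 6th dosed) gives 54% down to 10%. These figures rest on assumed rates, look sizes and accrual, and they describe the automatic SRC evaluation only. They do not show that the signal would be hidden, that cohort safety goes unreviewed or that any efficacy result would be wrong.

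The missing unit and denominator need correcting whatever the rates turn out to be. Overall this is a cheap improvement to safety governance, worth making but not essential to the trial's validity.

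**What to change.** Keep the pooled check and the ongoing rule as they stand. Do not put a minimum number or an 8-week filter on the ongoing rule: it has neither now, and adding them would weaken it early in the trial.

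Add to 10.4.1, with a cross-reference in 7.1.1 and 10.4.4:

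> The SRC will also evaluate the data if, in any one cohort with at least 12 dosed participants, more than one third have discontinued for a related AE.

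State in 10.4.1 whether the pooled 25% is taken over all dosed participants or only those with 8 weeks' opportunity, and name the unit of the ongoing rule in 7.1.1 and 10.4.4. If the redacted text or the Charter already contains a cohort check, only this wording is needed.

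The one-third limit and the minimum of 12 are suggestions. A 25% cohort limit catches more, but its extra reviews when no cohort truly exceeds 25% (step 4) make it optional.

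The cost is wording in three sections and the Charter, plus a few more SRC evaluations. No new data are needed, and any pause stays optional.
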